STATISTICAL ANALYSIS PLAN

Study name	Understanding Non-Response in Spine Fusion Surgery
Principal investigators	[name], MPH
Project lead	[name], MPH
Document Date	2/6/2019
Team conducting analysis	[name], MS [name], MPH
Version	3

AIM 1

We will assess baseline covariates with respect to the primary outcome, the Oswestry Disability Index (ODI) failure to achieve at least a 15% improvement (minimal important clinical difference as established by the Food and Drug Administration [FDA]) in the ODI score which ranges from 0 to 100 where 0 indicates not disability and 100 indicates complete disability when comparing baseline to six months after surgical procedure, reporting proportions for categorical variables and means and other measures of central tendency for continuous variables. We will use a multivariate logistic regression model with robust standard errors to evaluate these covariates and the primary outcome. A latent class analysis will be used to identify clusters of traits (e.g., patients with depression, anxiety, and catastrophizing) that tend to be grouped together within patient subtypes. This technique assumes there are distinct patterns and that individuals can be grouped into a small number of clusters representing each outcome path (the “latent classes”). The association between clusters and non-response will be described using logistic regression models accounting for repeated testing. As a sensitivity analysis, we will repeat the latent class analysis on the raw percentage change of the primary outcome measure to examine the robustness of variables that define latent classes. We will also conduct a sensitivity analysis looking for different degrees of change in the primary outcome beyond the 15% threshold defined by the FDA. We will also conduct a missing data analysis to describe and characterize enrolled participants who do not provide further outcome measures due to attrition. We will conduct sensitivity analyses using 10-fold multiple imputation to assess the robustness of the results. We will create an imputation model with variables found to be predictive of missingness and data will be imputed to create 10 complete data sets. The results will then be combined across data sets with the using STATA (i.e., MI) statistical software packages.

As a sensitivity analysis, we will repeat the latent class analysis on the raw percentage change of the primary outcome measure to examine the robustness of variables that define latent classes. We will also conduct a sensitivity analysis looking for different degrees of change in the primary outcome beyond the 15pts threshold defined by the FDA. We will also conduct a missing data analysis to describe and characterize enrolled participants who do not provide further outcome measures due to attrition. We

will conduct sensitivity analyses using 10-fold multiple imputation to assess the robustness of the results.

We will assess baseline covariates with respect to ODI non-improvement at 60 days, reporting proportions for categorical variables and means and other measures of central tendency for continuous variables. A multivariate logistic regression model with robust standard errors will be used to evaluate these covariates and the primary outcome: ODI non-Improvement at 60 days.

Use a latent class analysis to identify clusters of traits (e.g., patients with depression, anxiety, and catastrophizing) that tend to be grouped together within patient subtypes. This technique assumes there are distinct patterns and that individuals can be grouped into a small number of clusters representing each outcome path (the “latent classes”). The association between clusters and non-response will be described using logistic regression models accounting for repeated testing.

AIM 2

For responders and non-responders, we will perform a descriptive analysis of radiographic characteristics and compare proportions for categorical variables and means for continuous variables. We will explore the associations between radiographic measures and non-response using conditional logistic regression models, as appropriate for matched case-controls studies with multiple controls.

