STUDY PROTOCOL

Study name	Understanding Non-Response in Spine Fusion Surgery
Principal investigator	[name], MPH
Project lead	[name], MPH
Document Date	2/6/2019

CONTENTS

Study protocol	1
Abstract.....	2
Objective	2
Design.....	2
Recruitment Workflow Notes	2
Original Recruitment Design	3
Data Collection Design	4
Methods.....	4
Likely impact	5

ABSTRACT

There is considerable debate about the effectiveness of spine fusion surgery for degenerative disc disease (DDD) and other diagnoses related to chronic back pain. As many as 1-in-3 patients who undergo spine fusion do not report improvements in pain or functional status. Additionally, there are currently no evidence-based selection criteria to help surgeons determine which patients will respond to spine fusion surgery and which will not benefit.

The goal of this study was to better understand which patients are more likely to benefit from spinal fusion surgery. The Comparative Effectiveness Research Translation Network (CERTAIN) Spine Fusion Study partnered with spine surgery clinics to invite patients to participate in research activities designed to identify the impact of spine fusion surgery on the outcomes that matter most to patients. As part of this study, patients took surveys before and after their spine fusion surgery, and shared elements of their medical records for review. CERTAIN anticipated that this study would produce a paradigm that clinicians can use with patients to determine whether spine fusion surgery is right for them and identify any modifiable risk factors that may impact their response to surgery.

OBJECTIVE

Determine patient characteristics associated with non-response among patients undergoing lumbar fusion for DDD.

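### The SAP gives the non-response threshold as both 15% and 15 points, with no formula, so the primary outcome is not fixed

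*SAP*

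**What the plan says.** The first paragraph of SAP Aim 1 defines the primary outcome, measured from baseline to six months, as "failure to achieve at least a 15% improvement (minimal important clinical difference as established by the Food and Drug Administration [FDA". The same sentence places it "in the ODI score which ranges from 0 to 100 where 0 indicates not disability and 100 indicates complete disability". Later in that paragraph a sensitivity analysis is to look for "different degrees of change in the primary outcome beyond the 15% threshold defined by the FDA".

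The second paragraph of Aim 1 repeats that sensitivity-analysis sentence with a different unit: "different degrees of change in the primary outcome beyond the 15pts threshold defined by the FDA".

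Both wordings stand in the body of SAP Version 3, not in a change log. Neither comes with a formula or denominator. Aim 1 also says that "we will repeat the latent class analysis on the raw percentage change of the primary outcome measure", again without a formula. Aim 2 compares responders with non-responders and gives no definition of its own. The protocol states no ODI threshold and refers to the SAP for statistical methods.

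**The concern.** A 15% improvement between two visits can mean 15% of the patient's own baseline score, or 15% of the 0–100 range, which is 15 points. These are different rules for every patient with a baseline below 100. An analyst could code either one and claim to have followed the SAP.

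Non-response is the dependent variable in the Aim 1 logistic models and in the latent-class associations, and it decides who is a case and who a control in Aim 2. The unit therefore determines the headline non-response rate and the membership of both groups. It can also affect which traits appear to be associated with non-response.

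Timing adds to this. The protocol carries the same date as the SAP and reports in the past tense that "patients took surveys before and after their spine fusion surgery". That does not show that anyone had looked at outcomes, but it leaves open that the unit could be chosen with outcome data in hand.

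**Working it through.** **Inputs from the documents.** ODI range 0–100, and a threshold written as 15% and as 15pts (SAP Aim 1). The plan gives no event rate, sample size or ODI distribution, so it has no figure of its own to reproduce. The Abstract's "As many as 1-in-3 patients who undergo spine fusion do not report improvements in pain or functional status" is tied to neither rule.

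**Step 1: the two rules.** Let B be baseline ODI and D = B − follow-up ODI.

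- Relative rule: non-responder if D < 0.15 × B.
- Points rule: non-responder if D < 15.

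The rules disagree when 0.15 × B ≤ D < 15, a band 15 − 0.15 × B points wide.

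| Baseline ODI | Relative rule needs | Points rule needs | Width of disagreement |
|---|---|---|---|
| 30 | 4.5 | 15 | 10.5 |
| 45 | 6.75 | 15 | 8.25 |
| 60 | 9 | 15 | 6 |
| 100 | 15 | 15 | 0 |

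A fall from 50 to 40 is a 20% improvement (responder) but only 10 points (non-responder). Because 0.15 × B never exceeds 15, reclassification goes one way: some relative-rule responders become points-rule non-responders, never the reverse. Below baseline 15 the points rule cannot be met.

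This step needs no assumptions. The next three do.

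**Step 2: fixed baseline, assumed normal change.** With B = 50, mean change 15 and SD 18:

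- relative rule: Φ((7.5 − 15)/18) = Φ(−0.417) = 34% non-response;
- points rule: Φ((15 − 15)/18) = Φ(0) = 50%.

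Over baseline 30–60, mean change 10–20 and SD 15–18, between 12% and 27% of patients change category.

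**Step 3: a whole cohort, simulated.** Assumed: baseline mean 35–55, SD 12 or 16, truncated to 0–100; follow-up regressed on baseline with slope 0.5 and residual SD 14, bounded to 0–100. The mean change was set so that one rule gave one-third non-response.

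| Rule set at 33% | Other rule gives | Change category |
|---|---|---|
| Relative | 51–60% (points) | 17–26% |
| Points | 11–18% (relative) | 15–22% |

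With slope 0.3–0.7 and residual SD 10–18 (54 scenarios: three baseline means, two SDs, three slopes, three residual SDs), the first row becomes 47–70% with 13–37% changing, and the second 6–22% with 12–27% changing. Leaving follow-up unbounded narrows 11–18% to 13–18%. The share with baseline below 15 runs from under 0.1% to 9%.

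**Step 4: associations.** Assumed: baseline mean 45, SD 14, and a trait that worsens follow-up ODI by 3 points per SD. Odds ratio for non-response per SD of the trait:

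| Model | Correlation of trait with baseline ODI | Relative rule | Points rule |
|---|---|---|---|
| Without baseline ODI | 0 | about 1.4 | about 1.4 |
| Without baseline ODI | 0.3 | about 1.2 | about 1.1 |
| Without baseline ODI | 0.5 | 1.06–1.08 | 0.91–0.95 |
| With baseline ODI | 0 to 0.5 | 1.41–1.49 | 1.41–1.44 |

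The ranges cover both calibrations, with follow-up bounded or unbounded. At correlation 0.5 the unadjusted association changes direction between the rules. With baseline ODI in the model the rules nearly agree.

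**The case against.** The strongest reply is that the conflict is only one of notation. The defining sentence names the 0–100 scale, 15% of that range is 15 points, and the second paragraph, citing the same FDA threshold, says points. On that reading the two wordings agree. It is a fair reading, but the SAP does not state it. An improvement expressed as a percentage and measured against baseline is at least as naturally read as relative, and the planned use of "we will repeat the latent class analysis on the raw percentage change of the primary outcome measure" keeps that reading open.

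Other points have some force:

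- The points wording occurs once, in a paragraph that largely duplicates the one before and may be unmerged draft text. That makes it easy to correct, but it is still in the current plan.
- Other degrees of change are already planned as a sensitivity analysis. That varies the cut-off, not the unit, and it is the very sentence that carries both units.
- Adjusted associations barely depend on the rule. This holds if baseline ODI is in the model, but the SAP does not list its covariates. The non-response rate and the Aim 2 groups depend on the rule either way.
- The study calls itself exploratory (protocol, Likely Impact). That softens the consequence. The same section says the findings are to inform decision makers.

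**Conclusion.** The concern holds. The SAP gives two units for the threshold behind its primary outcome and nothing reconciles them, so the classification rule is contradictory as written and must be corrected.

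The gap in required improvement (4.5 to 9 points against 15, for baselines of 30 to 60) is exact once 15% is read as relative. The share of patients reclassified, roughly 15–26% in the main scenarios and 12–37% in the wider ones, rests on assumed ODI distributions and indicates scale only. The change of direction in an association needs both a trait strongly correlated with baseline ODI and a model without baseline ODI. Nothing here says which threshold the FDA set; that source is not among the documents.

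**What to change.** 1. Check the cited FDA source and state one formula for non-response: either B − follow-up < 15 points, or (B − follow-up)/B < 0.15. If the ratio is chosen, say how a baseline of 0 is handled, since the ratio is then undefined.
2. Fix the formula before outcome data are examined. If they have already been examined, say so and show both rules side by side.
3. Correct both paragraphs of Aim 1 to match, and use the formula throughout Aims 1 and 2. The 60-day non-improvement outcome, which has no threshold now, needs the same statement.
4. Report the other rule as a named sensitivity analysis.
5. Name baseline ODI as a covariate in the Aim 1 model, because either rule is arithmetically tied to it. This may already be intended.
6. If the points rule is adopted, report how many patients had a baseline below 15 and so could not meet it.

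The cost is SAP wording and one extra analysis run. No new data are needed.

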- Tablets: Original grant depended on patients completing CERTAIN baseline for themselves via tablet in clinic waiting room, however, patients and staff had technical difficulty with tablets
- Time: not enough time in waiting room or during rooming process to complete the CERTAIN baseline, let alone SF screening and recruitment
- Variability: each CERTAIN clinical site implemented CERTAIN at a slightly different point in their workflow (i.e. in waiting room, after rooming, after surgery scheduling, etc.) which made it difficult to provide clinic staff with guidance about how to assist with enrollment
- QI vs. Research: by not classifying SF as a multi-site study with "engaged" sites, the flexibility to allow clinic staff to actively enroll patients was lost (the exception to this is Evergreen, who had separate IRB approval for a research-only approach to enrollment, not QI)

Data Collection Design

A combination of Quality Improvement (QI) databases and research databases were used to complete the final dataset for this study. Most hospitals in Washington (WA) State participate in a novel, prospective care surveillance initiative called Spine Surgical Care and Outcomes Assessment Program (Spine SCOAP) that allows benchmarking on the indications for, processes of care, clinical outcomes and changes in patient reported outcomes (PROs) including pain and function for patients undergoing spine surgery. Spine SCOAP's analytic group, the Comparative Effectiveness Research Translation Network (CERTAIN) assesses PROs at 60-90 days, 12 and 24 months. Spine SCOAP data was obtained through CERTAIN, and research data was collected directly from patients via email or mail, rather than in the clinic as originally proposed. These surveys included additional baseline, 60-day, and 1-year characteristics and the outcome measures to the original CERTAIN surveys through the DatStat platform.

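### No planned Aim 1 covariate model uses the size of ODI change; a supporting continuous model should sit beside the responder analysis

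*SAP*

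**What the plan says.** The outcome is measured on a fine scale, an "ODI score which ranges from 0 to 100", and is then reduced to a yes/no: "failure to achieve at least a 15% improvement (minimal important clinical difference as established by the Food and Drug Administration [FDA". The comparison runs from baseline to six months.

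- **Six-month covariate model (SAP, Aim 1, opening paragraph):** "We will use a multivariate logistic regression model with robust standard errors to evaluate these covariates and the primary outcome".
- **60-day covariate model (SAP, Aim 1, later paragraphs):** also logistic, on the "primary outcome: ODI non-Improvement at 60 days". That sentence gives no cut-off of its own.
- **Clusters and non-response (Aim 1):** logistic.
- **Sensitivity analysis on a continuous measure (Aim 1):** "we will repeat the latent class analysis on the raw percentage change of the primary outcome measure". This covers the latent class analysis only.
- **Sensitivity analysis on the threshold (Aim 1):** "looking for different degrees of change in the primary outcome beyond the 15% threshold defined by the FDA". No cut-offs and no model are named. When the SAP repeats the sentence further on, the threshold is 15 points instead of 15%.

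The Protocol's Objective is to find characteristics associated with non-response. The Rationale beneath it says the added measures will be evaluated for association with changes in function and pain at six months.

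**The concern.** Two things are lost when only the yes/no result enters the covariate models.

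The first is distinction between patients. Take a baseline ODI of 50 and the 15% reading. A patient who ends at 43 has improved by 7/50 = 14%, and a patient who ends at 80 is 30 points worse. Both are coded as non-response.

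The second is precision. Many traits are to be examined and neither document states a sample size or power, so a model that discards usable information may miss associations the same data could show. Trait results also come to depend on how many patients lie near the cut, and the SAP states that cut in two units.

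As the plan stands, nothing in it estimates the association with change in function that the Rationale describes.

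**Working it through.** The documents give no sample size, power, effect size or standard deviation, so there is no planned figure to reproduce. The check is how much a yes/no outcome costs under stated assumptions.

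**Inputs**
- Share of patients below the cut, p. The only related figure is in the Protocol Abstract: "As many as 1-in-3 patients who undergo spine fusion do not report improvements in pain or functional status". It is an upper figure for a different outcome, so p = 1/3 is an assumption, varied here from 0.20 to 0.50.
- Shape of ODI change: not given. Normal first, then others.
- Trait effect: assumed linear.

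**Step 1. Efficiency under normality.** Relative to the continuous outcome, a dichotomised normal outcome has efficiency E = φ(z_p)² / [p(1 − p)].

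At p = 1/3, z = −0.431 and φ = 0.3636, so E = 0.1322 / 0.2222 = 0.595. The loss is 40.5%, standard errors grow by 1/√0.595 = 1.30, and 1/0.595 = 1.68 times the patients are needed for equal precision.

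| p | E | Loss |
|---|---|---|
| 0.20 | 0.490 | 51.0% |
| 0.25 | 0.539 | 46.1% |
| 0.333 | 0.595 | 40.5% |
| 0.40 | 0.622 | 37.8% |
| 0.50 | 0.637 | 36.3% |

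**Step 2. What that means for power.** If the continuous model had 80% power (two-sided 5%), the binary model at p = 1/3 would have Φ[(1.960 + 0.842) × √0.595 − 1.960] = Φ(0.20) = 58%. From 90% it would fall to about 70%.

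**Step 3. Does normality matter?** Logistic and linear regression, both with robust standard errors, were compared by simulation (one trait, assumed correlation 0.2, assumed n = 200, 1,500 runs per setting). The loss is one minus the squared ratio of mean test statistics.

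| Shape of change | p = 0.20 | p = 1/3 | p = 0.50 |
|---|---|---|---|
| Normal | 53.4% | 43.9% | 43.7% |
| Heavy-tailed (t, 5 df) | 47.5% | 28.6% | 17.6% |
| Right-skewed (gamma) | 11.5% | 21.6% | 38.7% |

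There was a loss in every setting, but it ran from about 12% to 53%.

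**Step 4. The unit of the cut.** The SAP's two units give different values of p, and so different losses.

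| Baseline ODI | 15% equals | 15 points equals |
|---|---|---|
| 20 | 3 points | 75% |
| 50 | 7.5 points | 30% |
| 80 | 12 points | 18.8% |

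**The case against.** The strongest reply is that non-response is the study's question. The Objective, the Likely Impact section and Aim 2 are all framed around responders and non-responders, and any responder endpoint groups patients who worsened with those who nearly improved enough. A model of mean ODI answers a somewhat different question, and the efficiency figure is a like-for-like loss only if a trait shifts the whole distribution. This stands, and it is why the responder model should remain the headline. It does not remove the case for a supporting model, because the Rationale also promises association with change in function and no covariate model supplies it.

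A reader might also infer that the threshold sensitivity analysis only tries larger cut-offs. The SAP does not say so. The word beyond can mean other than, no values are named, and a cut near zero change could partly separate patients who worsened from near-misses. The fair criticism is that the analysis is unspecified and, as written, does not commit to a continuous model.

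Finally, a reader might take 40% as a property of this study. The documents do not support that: the one-third figure is not the share failing the ODI cut, and the shape of ODI change is not given.

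**Conclusion.** The point holds in a limited form. Every Aim 1 covariate model is logistic on a dichotomised ODI result, and the continuous change appears only in the latent class sensitivity analysis. The plan therefore leaves out an inexpensive analysis that its own Rationale calls for.

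The size is an assumption, not a finding. The loss is about 40% with normal change, a linear trait effect and one third below the cut. Under normality it is 36% to 51% for shares from 50% to 20%. Across the simulated shapes it is about 12% to 53%, and usually smaller when change is skewed or heavy-tailed. The share below the cut cannot be settled until the SAP says whether 15% or 15 points is meant.

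The documents do not support the stronger conclusion that the responder outcome is wrong or should be replaced. The change is worth making, but the headline analysis does not fail without it.

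**What to change.** Keep the responder model as the headline and keep the varied-threshold analysis. Add to SAP Aim 1 one prespecified supporting model at each analysed time point (six months and 60 days): a linear regression of follow-up ODI (0–100) on the same covariates, with baseline ODI as a term and robust standard errors. Report its estimates and confidence intervals beside the logistic results, labelled as supporting. State the unit of the 15 threshold once and use it throughout.

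Two tempting extensions should be left out.

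- **A mixed model over the survey visits.** The Protocol's Data Collection Design says "These surveys included additional baseline, 60-day, and 1-year characteristics and the outcome measures" and lists no six-month survey, while the primary outcome is at six months. A model over 60 days and 1 year would omit the primary time point. Reconcile the schedule first.
- **Calling a trait robust when both models agree in direction.** Both use the same patients. With E = 0.595 the two estimates correlate at about √0.595 = 0.77, so a trait with no effect would agree in sign about 1/2 + arcsin(0.77)/π = 78% of the time.

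The cost is one SAP paragraph and one further model per time point. The ODI scores are those the responder model already needs. The drawback is a second estimate per trait, so the SAP must say plainly that the binary result leads.

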Rationale: *A patient's sense of activation in managing their health, loci of control, tendency towards catastrophizing, social support, satisfaction with work, self-perceived quality of life, expectations, general mental health, anxiety and depression, and extent of critical medication (e.g., opioids, sleeping aids) use have been associated with clinical outcomes and self-perception of health status. These parameters have not been well studied among those who fail to improve with spine surgery compared to responders. Nearly all Spine SCOAP patients undergo baseline and follow up surveys of patient reported measures. We will perform a prospective cohort study adding standardized measures of personality traits and mental health and will evaluate their association with changes in function and pain at six months after surgery.*

DESIGN

Recruitment Workflow Notes

All site specific processes are in *italics*

UWMC and HMC:

- *Patients were identified from surgery schedules* (eligible if: lumbar fusion (L1-S1), over 18, English as primary language, not revision surgery, surgery date in > 10 days (not official study inclusion criteria, but needed to ensure enough time for mailers))
- *Research staff screened each patients EMR to confirm eligibility and noted in EMR disclosure log*

- Research staff sent each eligible patient a recruitment mailer containing: consent form (2), HIPAA Authorization Form (2), Study Intro Letter, Baseline survey, and a return envelope
- One week after mailer was sent, phone recruitment began; 5 calls over ~10 days
- During phone call: research staff delivered screening questions, reviewed forms, outlined which were copies for patient's own records and which to return, gave instructions on how to return
- Patient was enrolled when consent and baseline were returned via mail (HIPAA form return did not impact enrollment)

Proliance:

- Patients were identified from an automated feed delivered from Proliance IT via secure email once a week* (eligible if: lumbar fusion (L1-S1), over 18, English as primary language, not revision surgery, surgery date in > 10 days (not official study inclusion criteria, but needed to ensure enough time for mailers))
- *Research staff screened schedule for potentially eligible procedures and noted in EMR disclosure log, even though Proliance EMR was not accessed at this time*

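### The SAP names two primary time points for ODI non-response, six months and 60 days, ranks neither, and no described survey falls at six months

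*SAP*

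**What the plan says.** SAP Aim 1, opening paragraph: the primary outcome is "failure to achieve at least a 15% improvement" in ODI, a score running from 0 to 100, "when comparing baseline to six months after surgical procedure". The Rationale under the protocol's Objective matches this: the study will "evaluate their association with changes in function and pain at six months after surgery".

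SAP Aim 1, later paragraph, same version 3: a logistic model with robust standard errors is specified for "the primary outcome: ODI non-Improvement at 60 days". This sentence gives no cut-off.

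Protocol, Data Collection Design: CERTAIN "assesses PROs at 60-90 days, 12 and 24 months". Of the research surveys it says: "These surveys included additional baseline, 60-day, and 1-year characteristics and the outcome measures to the original CERTAIN surveys".

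On missing data, the SAP plans a multiple-imputation sensitivity analysis in which "data will be imputed to create 10 complete data sets".

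On the cut-off, the sensitivity-analysis sentence in the opening paragraph looks at degrees of change "beyond the 15% threshold defined by the FDA". The same sentence is repeated further on with 15 points in place of 15%. Aim 2 compares responders with non-responders and names no time point.

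**The concern.** Non-response is the dependent variable of the Aim 1 regression and of the latent-class association, and it forms the case and control groups of Aim 2. If its time point is open, two analysts who both follow version 3 can label the same patient differently. Non-response at 60 days and at six months are different outcomes, and a reader could not tell which of them the reported patient profile describes.

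The six-month version has a further problem: the documents describe no survey that would supply it.

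The protocol also describes the surveys in the past tense, and neither document says whether outcome data had been examined when either definition was written. This is not evidence that they had been. It does mean that a reader cannot rule out a choice of time point made after seeing the results.

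**Working it through.** The documents give no sample size, power, alpha or event rate, so there is no planned figure to reproduce. The check sets the outcome definitions against the data schedule and then works through the cut-off.

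**1. Time points named for the outcome**

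| Place | Time point | Status given |
|---|---|---|
| Protocol, Objective, Rationale | six months | aim of the cohort study |
| SAP Aim 1, opening paragraph | six months | primary |
| SAP Aim 1, later paragraph | 60 days | primary |
| SAP Aim 2 | none stated | not applicable |

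No sentence ranks the two or says that one replaces the other. The SAP's only multiplicity wording concerns the association between clusters and non-response. It does not choose between time points.

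**2. Time points with a described survey** (protocol, Data Collection Design)

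Six months = 365.25 / 2 = 182.6 days.

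| Described assessment | Distance from six months |
|---|---|
| 60-day research survey | 182.6 - 60 = 122.6 days before |
| End of the 60-90 day CERTAIN window | 182.6 - 90 = 92.6 days before |
| 1-year / 12-month survey | 365.25 - 182.6 = 182.6 days after |
| 24-month CERTAIN survey | later still |

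No analysis window is given that would map any of these to six months. The described number of six-month ODI values is therefore zero. Multiple imputation needs some observed values of the variable to fit its model, so it cannot fill this gap.

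**3. Cut-off**

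*If 15% means percent of the scale:* 0.15 x 100 = 15 points at every baseline. The two wordings agree.

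*If 15% means relative change:* the required fall is 0.15 x baseline. The wordings disagree for falls from that value up to just under 15 points. The baselines below are illustrative, since the documents give no ODI distribution.

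| Baseline ODI | Fall needed under 15% | Falls classified differently |
|---|---|---|
| 20 | 3 | 3 to <15 |
| 40 | 6 | 6 to <15 |
| 60 | 9 | 9 to <15 |
| 80 | 12 | 12 to <15 |
| 100 | 15 | none |

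Example: a change from 40 to 30 is 10 points, or 10 / 40 = 25%. It is a response under the relative reading and a non-response under 15 points. A patient with a baseline below 15 could never respond under 15 points, and the inclusion criteria set no ODI minimum.

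The text permits both readings. The outcome definition mentions the 0-100 range, and the sensitivity analysis refers to raw percentage change.

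**The case against.** The strongest reply is that this is drafting residue and not two planned primary outcomes. The second half of Aim 1 repeats sentences from the opening paragraph almost word for word. The Rationale is in the future tense, while the surrounding protocol is in the past tense and says that collection departed from the original proposal. On this view six months is left-over proposal text and 60 days is the working plan. That may be so, but the SAP does not say it, and both statements stand in the current version.

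A second reply is that the Data Collection Design is a short narrative and may not list every survey. That is fair, and it limits the claim: no six-month survey is *described*. If one was run, the remedy is to add it.

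A third is that 15 points on the scale is the natural reading of the cut-off, because the 0-100 range stands beside the percentage and the repeated sentence says points. This has force. The cut-off is the lesser part of the concern and may need only a statement of units. The 60-day sentence, however, carries no cut-off at all.

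Finally, the study calls itself exploratory. That removes any argument about a confirmatory error rate, and none is made here. An exploratory study still needs a dependent variable that is defined and can be computed.

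**Conclusion.** The concern holds, and the text must be corrected before the main result can be interpreted. One SAP version states two primary time points without ranking them. The one that matches the protocol's Rationale has no described data source, so on the described schedule it is missing for all patients. This rests on the Data Collection Design being a complete account of the surveys; an unlisted six-month survey would remove the data gap but not the conflict between the two definitions.

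The cut-off matters only if 15% is relative change. In that case the classification differs over a band that narrows as baseline rises, from 3 to under 15 points at a baseline of 20 to nothing at 100. How many patients fall in that band cannot be worked out from the documents.

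**What to change.** 1. Name one primary time point that corresponds to a survey actually collected with ODI, and give its window in days. Align the Rationale, the Data Collection Design, both parts of SAP Aim 1 and the Aim 2 groups to it.
2. On the described schedule, 60 days is the only one of the two labelled primary time points with a survey. If it is kept, state whether the 60-day research survey, the 60-90 day CERTAIN survey or both count, limit the conclusion to early non-response, and remove the six-month outcome. One year also has described surveys and could be named instead, with a reason.
3. If a six-month survey was collected, add it to the Data Collection Design, keep six months as primary and label 60 days secondary.
4. In every case confirm that ODI was collected at the chosen survey, since the protocol speaks only of PROs and outcome measures.
5. State one cut-off with its scale (percent of baseline, or points on 0-100) and apply it at each analysed time point. Delete the duplicated sensitivity-analysis and latent-class text, and say that the sensitivity, missing-data and imputation plans apply to the retained primary outcome.
6. Add a dated note on whether the choice was made before outcome data were examined. If it was not, call it post hoc.

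The cost is wording in both documents, one data check and the note, with no new data collection and no added analysis. The downside is a narrower claim if 60 days is chosen: the study would no longer address the six-month change that its Rationale sets out.
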